**Protocol Amendment Summary of Changes Table**

DOCUMENT HISTORY	
Document	Date
Amendment 1	04 FEB 2020
Original Protocol	19 MAR 2019

**Amendment 1 (04 FEB 2020)**

This amendment is considered to be substantial based on the criteria set forth in Article 10(a) of Directive 2001/20/EC of the European Parliament and the Council of the European Union, as it includes a new criterion for premature termination of the study. Nevertheless, it neither significantly impacts the safety or physical/mental integrity of participants nor the scientific value of the study.

**Overall Rationale for the Amendment:**

This amendment was prepared to incorporate Health Authority feedback regarding the definitions for both the end of study and adverse events, assess body weight at additional visits, and to clarify the number of times a participant may be rescreened.

Section # and Name	Description of Change	Brief Rationale
1.3 Schedule of Activities 8.2.2 Physical Examinations 10.4.4 Visit 4 – ED 50-75 (Month 6 ± 14 days) 10.4.6 Visit 6 if needed – ED 50-75 (Month 18 ± 14 days)	Body weight measurement has been added to Visits 4 and 6.	Body weight will be assessed every 6 months in order to avoid underdosing.
4.4 End of study definition	Definition for the end of the overall study changed. The end of the overall study is defined as LPLV and the last data from the last visit are received. For each participating country, end of study is achieved with LPLV in that country.	Align end of study with planned trial activities for participants.
4.4 End of Study Definition	Criteria added for premature termination of the study.	Define stop criteria for premature termination of the study.
5.4 Screen Failures	Section updated to specify that screen failures may be rescreened once.	Define maximum number of times a participant may be rescreened.
6.2 Preparation/Handling/Storage/Accountability	Instructions updated to more accurately describe the instructions for management of study intervention.	Reflects current sponsor standard.
10.1.1 Regulatory and Ethical Considerations	References to region-specific laws removed	Remove redundancy, as these laws are covered by "...all other applicable local regulations."

Section # and Name	Description of Change	Brief Rationale
10.2 Appendix 2: Clinical Laboratory Tests	Addition of albumin/creatinin ratio, Beta-2microglobulin.	Clarification that the biomarker albumin will be assessed through the albumin/creatinine ratio. Beta-2microglobulin was erroneously identified as alpha-2microglobulin.
10.3.1 Definition of AE	Requirements for laboratory test results modified	Agency request
10.3.4 Reporting of SAEs	Reporting instructions updated to refer to email instead of facsimile transmission.	Reflects current sponsor standard.

Typographical, grammatical, and other minor edits are not identified.

## 1. Protocol Summary

### 1.1 Synopsis

**Protocol Title:** Post-marketing investigation (PMI) to assess safety and efficacy of Jivi (BAY 94-9027) treatment in participants with hemophilia A

**Short Title:** Jivi interventional study to assess safety and efficacy

**Rationale:** This study aims to collect clinical data in at least 25 participants, to comply with the post-marketing requirements to collect safety data of 200 participants treated with at least 100 exposure days (ED) including participants from pre-authorization studies, according to EMA FVIII guideline requirements EMA/CHMP/BPWP/144533/2009 rev.2 ([EMA 2017](#)).

### Objectives and Endpoints:

Objectives	Endpoints throughout the study
Primary 

To assess safety of Jivi

	
Primary Endpoint
 

FVIII inhibitor development by the Nijmegen Bethesda assay.

 
Secondary Endpoints
 

Treatment-emergent adverse events (TEAE)

Development of treatment-emergent anti-PEG antibodies

Secondary 

To assess clinical efficacy of Jivi

	
Secondary Endpoint
 

Annualized bleeding rate (ABR)

### Overall Design:

The study will be a multicenter, single group, uncontrolled open-label trial. Severe hemophilia A patients, age  $\geq 18$  years, will be enrolled and treated with prophylaxis treatment and for breakthrough bleeds for at least 100 exposure days (ED), which may require 1-2 years depending on the prophylaxis regimen. Assessment of immunogenicity/safety will be performed at pre-defined ED as required by the EMA FVIII Guideline. The recommended starting dose is every 5 days treatment (45 IU/kg). Response to treatment will be assessed at the next visit after 10-15 ED, scheduled for inhibitor assessment as per Guideline. Participants may be assigned to different dosing regimens (every 7 days or 2x/week) or continue with every 5 days regimen, according to individual bleeding tendency and needs at investigator's discretion. Clinical general safety, efficacy, and immunogenicity will be assessed at baseline, 10-15 ED, 50-75 ED and after approximately 100 ED.

This study will address regulatory requirements of assessment of safety in a total of 200 participants with 100 ED including pre-licensure participants of the development program from the studies #13024 Protect VIII and #15912 Protect Kids. This study will include at least 25 participants for fulfillment of the requirement and provide a pooled analysis of all clinical studies (phase III/IV) including at least 200 participants observed for at least 100 ED.

The study will assess the important identified risks of development of Factor VIII (FVIII) inhibitors, hypersensitivity, and potential lack of drug effect associated with anti-polyethylene glycol (PEG) antibodies during the first exposures to Jivi and long-term treatment up to 100

ED. An optional interim analysis will be performed, if needed for regulatory submission or publication purposes, after all participants have been treated for 6 months.

**Intervention Model:** Single Group

**Primary Purpose:** Treatment

**Number of Arms:** Single arm

**Masking:** No masking

**Number of Participants:** Approximately 25-30 participants will be assigned to the study intervention. At least 25 participants are expected to complete the study. The study is completed when 25 participants have reached 100 ED.

**Intervention Groups and Duration:**

All participants will be treated with three possible prophylactic regimens: 2x/week, every 5 days, or every 7 days with a recommended starting regimen of every 5 days. Participants are allowed to change the dose frequency during the study. All treatment decisions for identifying appropriate prophylactic treatment regimens should be guided by clinical judgement based on individual participant characteristics and treatment response.

The total treatment duration is the time to reach 100 exposure days (ED) of Jivi. The total duration of study participation for each participant may require up to 2 years depending on the selected prophylactic regimen. After the end of the study, the participants will be offered the option to participate in a non-interventional PASS study. While the decision for dose adjustment is at the investigator's discretion based on patient clinical characteristics, the following recommendations are provided: the starting dose is 45 IU/kg every 5 days.

Investigator may assess if dose regimen adjustment is warranted at the next planned visit (10-15 ED). A participant with zero bleed during the first 8-10 weeks of treatment may be considered for every 7 days at 60 IU/kg; a participant with 1 clinically relevant bleed during the first 8-10 weeks may be considered to either continue treatment every 5 days while at the 60 IU/kg or switch to twice weekly at 40 IU/kg; and a participant with  $\geq 2$  clinically relevant bleeds during the first 8-10 weeks should be changed to twice weekly at 40 IU/kg.

[figure not shown]
The details about duration and recommended dose regimen of study participation are as follows:

**Recommended dose regimen**

Procedure	Duration	Dose regimen	Route of administration
Screening	> 2 weeks, ≤ 8 weeks	Continuation of previous treatment	
	Time to reach 10- 15 ED (8 to 10 weeks)	Recommended starting dose 45 IU/kg every 5 days. Dose regimen can be adjusted any time in case of bleeds	IV injection
	0 bleed during the first 8-10 weeks:	Recommended dose regimen: 60 IU/kg every 7 days	
Treatment Phase	Time to reach 100 ED	1 clinically relevant bleed during the first 8-10 weeks:  ≥ 2 clinically relevant bleeds during the first 8-10 weeks:	Continue every 5 days at dose of 60 IU/kg  Or at investigator's judgement: Switch to 40 IU/kg 2x/week  Change to 40 IU/kg 2x/week

ED = exposure day, IV = intravenous

Clinically relevant: joint or muscle bleed that need treatment

**Data Monitoring Committee:** No**1.2 Schema****Figure 1-1 Schema for suggested dose changes in response to bleeding**

ED = exposure day

Clinically relevant: joint or muscle bleed that need treatment

Note: Participants are allowed to change the dose regimen during the study. All treatment decisions for identifying appropriate prophylactic treatment regimens should be guided by clinical judgement based on individual patient characteristics and treatment response

## 1.3 Schedule of Activities (SoA)

Table 1-1 Study Schedule of Activities (SoA)

Procedures	Screening a	Baseline Pre-dose	ED 10-15	ED 50-75 Every 6 months			End of study 100 ED / Early Termination
	Visit 1 2-8 Wks before baseline	Visit 2 Day 1	Visit 3 Wk 8-10 b	Visit 4 Month 6 (±14 days) c	Visit 5 Month 12 (±14 days) c	Visit 6 Month 18 if needed (±14 days) c	Last Visit (+14 days)
Informed consent (inclusion )	X						
HIV screening d	X						
Inclusion and exclusion criteria	X	X					
Demography(including gene defect)	X						
Full physical examination including neurological standard assessment, height, and weight	X						X
Body Weight Measurement				X	X	X	
Activity level (type of sports, hrs/wk)	X						
Medical and surgical history (general, disease, family history of hemophilia, and history of inhibitor)	X						
Activity tracker	X	X		X	X		X e
Previous medication (medication history)	X						
Dose regimen adjustment			X				
Vital signs f	X	X					X
Urine sample (routine urinalysis and renal biomarkers)	X	X			X		X
Laboratory assessments (Hematology and clinical chemistry,)	X				X		X
PEG level in plasma	X						X
Immunogenicity (Factor VIII inhibitor, ADA) g	X	X	X	X	X		X

**Table 1-1 Study Schedule of Activities (SoA)**

Procedures	Screening a	Baseline Pre-dose	ED 10-15	ED 50-75 Every 6 months			End of study 100 ED / Early Termination
	Visit 1 2-8 Wks before baseline	Visit 2 Day 1	Visit 3 Wk 8-10 b	Visit 4 Month 6 (±14 days) c	Visit 5 Month 12 (±14 days) c	Visit 6 Month 18 if needed (±14 days) c	Last Visit (+14 days)
Recovery (pre and 15-30 min post injection FVIII levels) h		X	X				X
FVIII level after 48 or 72 hours after last injection				X	X		
In-hospital injection of Jivi		X	X				X
AE review	X	X	X	X	X	X	X
Return used and unused study intervention			X	X	X	X	X
Dispense study intervention for home injections			←==continuously in accordance with IxRS drug dispensing schedule==→				
Injection of Jivi			←=====continuously in accordance with assigned treatment regimen=====→				
Concomitant medication review	X		←=====continuously=====continuously=====→				
Patient diary (EPD) documentation	X		←=====continuously=====continuously=====→				
Interaction between participants and investigators			←=====Monthly contact=====→				

Abbreviations: ADA=anti-drug antibody, AE=adverse event, ALT=alanine aminotransferase, AST=aspartate aminotransferase, ED=exposure days, EPD=electronic patient diary, HIV=human immunodeficiency virus, hrs=hours, IxRS=Interactive voice/web response system, max=maximum, and Wk=week.

- The time interval between Screening and Baseline visit is 2 to 8 weeks.
- Although the allowable visit window is ±14 days, visits must occur within the specified ED range.
- Visits should be scheduled within the visit window so that at least one visit occurs in the 50 – 75 ED range.
- HIV screening will be performed only in case that negative result in patient documentation is older than 1 year at date of screening.
- Only in case of Early Termination Visit before V6.
- In case of any injection related AE, vital signs will be collected in addition post-injection for participants.
- At Baseline, Visit 3 and End of Study/Early Termination Visit, blood samples for immunogenicity will be collected before the in-hospital injection of Jivi.
- Recovery should be measured at least 72 h after last injection of FVIII of Jivi.

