### 4. Study Design

#### 4.1 Overall Design

The study will be a multicenter, single group, uncontrolled open label trial. Severe hemophilia A patients, age  $\geq 18$  years, will be enrolled and treated with prophylaxis treatment and for breakthrough bleeds for at least 100 ED, which may require 1-2 years depending on the

prophylaxis regimen. Assessment of immunogenicity/safety will be performed at pre-defined ED as required by EMA FVIII Guideline.

The recommended starting dose is every 5 days treatment (45 IU/kg)- An assessment of response to treatment will be performed at the next scheduled visit after 10-15 ED (8-10 weeks). Thereafter, participants may be assigned to different dosing regimens (every 7 days or 2x/week) or continue with every 5 days regimen, according to individual bleeding tendency and needs at investigator's discretion. Clinical general safety, efficacy, and immunogenicity will be assessed at baseline, after 10-15 ED, 50-75 ED and after approximately 100 ED.

This study will address regulatory requirements of assessment of safety in a total of 200 participants with 100 ED including pre-licensure participants of the development program from the studies #13024 Protect VIII and #15912 Protect Kids. This study will include at least 25 participants for fulfillment of the requirement and provide a pooled analysis of all clinical studies (phase III/IV) including at least 200 participants observed for at least 100 ED.

The study will assess the important identified risks of development of Factor VIII (FVIII) inhibitors, hypersensitivity, and potential lack of drug effect associated with anti-polyethylene glycol (PEG) antibodies during the first exposures to Jivi and long-term treatment up to 100 ED.

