### **Intervention Groups and Duration:**

Participants will be enrolled in the study and start the recommended starting treatment with every 5 days at a dose of 45 IU/kg. Participants with an increase in bleeding frequency may switch to a twice weekly regimen (2x/week, 40 IU/kg) at the investigator's discretion during the first 8-10 weeks.

At the next scheduled visit (after 10-15 ED, 8-10 weeks), all participants will have their bleeding frequencies reviewed by the investigator to determine any adjustment of the treatment. Participants who have no bleeds during the first 8-10 weeks are recommended to have the treatment with every 7 days at a dose of 60 IU/kg. Participants who have 1 clinically relevant bleed (e.g. joint or muscle bleed) during the first 8-10 weeks may continue the treatment with every 5 days at dose of 60 IU/kg; the regimen may also be adjusted to 2x/week (40 IU/kg) at the investigator's discretion after evaluation of bleed risk. If participants have  $\geq$  2 relevant bleeds during the first 8-10 weeks, these participants should change treatment to 40 IU/kg 2x/week. For overweight patients, the maximum total dose per injection should not be higher than approximately 6000 IU (rounded up to full vials).

Participants are allowed to change the dose frequency at any time during the study in case of increase in bleeding frequency. All treatment decisions for identifying appropriate prophylactic treatment regimens should be guided by clinical judgement based on individual participant characteristics and treatment response. It is recommended that the participant increases frequency (if treated every 7 days or every 5 days) after a second spontaneous bleed within a 3-month period.

The total treatment duration is the time to reach 100 (exposure days) ED of Jivi. The total duration of study participation for each participant may require up to 2 years depending on the selected prophylactic regimen. The details about duration and recommended dose regimen of study participation for each study periods are as follows:

Procedure	Duration	Dose regimen	Route of administration
Screening	> 2 weeks, ≤ 8 weeks	Continuation of previous treatment	
	Time to reach 10-15 ED (8 to 10 weeks)	Recommended starting dose 45 IU/kg every 5 days. Dose regimen can be adjusted any time in case of bleeds	IV injection
	0 bleed during the first 8-10 weeks:	Recommended dose regimen: 60 IU/kg every 7 days	

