#### **9.5 Interim Analyses**

An optional interim analysis will be performed, if needed for regulatory submission or publication purposes, after all participants have been treated for 6 months for assessment of the main safety (inhibitor development) and efficacy endpoints. The risk for inhibitor development is highest during the first 20-50 ED. After this timepoint, the study would be continued according to the study design and protocol.

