#### **10.4.4 Visit 4 – ED 50-75 (Month 6 ± 14 days)**

This visit should take place approximately 48 or 72 hours (if not possible then 96 hours) after the last injection of Jivi.

- Ask the participant to wear activity tracker for continuous 2-3 weeks after Visit 4 (Month 6) before Visit 5 (Month 12)
- Body weight measurement
- Concomitant medication review
- AE review
- Blood samples for (see details in [Table 10-1](#)):
  - Immunogenicity testing
  - FVIII level
- Dispense study intervention for home injections in accordance with IxRS drug dispensing schedule
- Return used and unused study intervention
- Check of EPD entries and bleeding history
- Continue regular monthly contact between participant and the site to check EPD documentation and AE review until the End of Study/Early Termination

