#### **10.4.6 Visit 6 if needed – ED 50-75 (Month 18 ± 14 days)**

- Body weight measurement
- Concomitant medication review
- AE review
- Dispense study intervention for home injections in accordance with IxRS drug dispensing schedule
- Return used and unused study intervention
- Check of EPD entries and bleeding history
- Continue regular monthly contact between participant and the site to check EPD documentation and AE review until the End of Study/Early Termination

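### Participants who change to twice-weekly dosing at roughly Months 2.5 to 9.7 (from every 5 days) or 2.5 to 6.6 (from every 7 days) have no scheduled inhibitor sample at ED 50-75

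*Protocol*

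**What the plan says.** Protocol section 4.1 commits to testing by exposure: "Clinical general safety, efficacy, and immunogenicity will be assessed at baseline, after 10-15 ED, 50-75 ED and after approximately 100 ED". FVIII inhibitor development is the primary endpoint.

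The schedule is set by calendar. The Table 1-1 column header over Visits 4, 5 and 6 reads "ED 50-75 Every 6 months". Appendix 4 repeats the label from "ED 50-75 (Month 6 ± 14 days") for Visit 4 through to "ED 50-75 (Month 18 ± 14 days") for Visit 6. The footnote marked on these three visits (footnote c) says: "Visits should be scheduled within the visit window so that at least one visit occurs in the" 50-75 ED range. The stricter footnote, under which a visit must fall in its ED range, is marked on Visit 3 only.

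Inhibitor and antibody samples are drawn at Visits 4 and 5 but not at Visit 6 (Table 1-1; Protocol 8.2.1).

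Dosing starts at every 5 days and may move after Visit 3 to every 7 days or twice weekly. Later changes are also open: "Participants are allowed to change the dose frequency at any time during the study in case of increase in bleeding frequency".

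**The concern.** A month-based visit matches an ED range only for some dosing frequencies. Here the frequency differs between participants and may change during follow-up. If exposure runs from below 50 to above 75 between two sampling visits, a site can keep every window and still miss the sample that section 4.1 promises.

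The participants exposed to this are those who bleed more and increase their frequency. The gap would also be hard to see in the output. SAP 4.3 counts missing inhibitor measurements, but a Visit 4 sample taken at ED 42 is not missing. SAP 6.4 lists the ED before each measurement only for participants with a positive result. A negative result outside the range could therefore stand under a visit labelled ED 50-75. With 25 participants required to reach 100 ED, even a few such cases would count.

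**Working it through.** **Inputs.** Dosing intervals are 5, 7 and 3.5 days (twice weekly), and Visit 3 is at Week 8-10 (days 56-70), from Protocol 4.1 and Table 1-1. An ED is a calendar day with at least one infusion (SAP 6.1). Assumptions: a month is 30.44 days, adherence is full, and there are no bleed-treatment ED. The windows are then days 168.6-196.6 (Visit 4), 351.3-379.3 (Visit 5) and 533.9-561.9 (Visit 6).

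**Formula.** x(t) = sum over dosing periods of (days in period / interval). ED(t) = 1 + whole part of x(t), because the first infusion on day 0 is ED 1.

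**The plan's other figures reproduce.** On every 5 days, day 56 gives 1 + 11 = 12 and day 70 gives 1 + 14 = 15, inside the stated 10-15. Reaching 100 ED takes 99 × 3.5 / 365.25 = 0.95 years, 99 × 5 / 365.25 = 1.36 years or 99 × 7 / 365.25 = 1.90 years, close to the stated 1-2 years.

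**ED across each window:**

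| Regimen | Visit 4 | Visit 5 | Visit 6 |
|---|---|---|---|
| Every 5 days | 34-40 | 71-76 | past 100 |
| Every 7 days after Visit 3 | 28-33 | 54-59 | 80-85 |
| Twice weekly from Visit 3 | 43-52 | 95-104 | past 100 |

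The label reproduces at Month 12 for the two less frequent regimens. It does not at Month 18, and at Month 6 it does so only at the end of the twice-weekly window. On twice weekly from Visit 3, ED 50 falls at about day 189.5 (Visit 3 at day 56) to day 192.5 (Visit 3 at day 70). That leaves about 4 to 7 days before the Visit 4 window closes.

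**Why switchers miss.** From the close of Visit 4 to the opening of Visit 5 is 351.3 − 196.6 = 154.7 days, or 154.7 / 3.5 ≈ 44 ED on twice weekly. The target range is only 26 ED wide. Someone who changes just as the Visit 4 window closes has about ED 40 (from every 5 days) or ED 32 (from every 7 days). Adding 44 gives 84 or 76, already past 75.

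**Limits for a switch on day s.** Both visits miss if ED is below 50 when Visit 4 closes, x(196.6) < 49, and above 75 when Visit 5 opens, x(351.3) ≥ 75.

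- From every 5 days: x = s/5 + (t − s)/3.5 = t/3.5 − 0.0857s. The first condition gives 56.2 − 0.0857s < 49, so s > about 84. The second gives 100.4 − 0.0857s ≥ 75, so s ≤ about 296. Counting whole infusions day by day gives days 81-295 (215 days). Counting fractional ED from zero puts the lower limit at day 73. So the interval is roughly Months 2.5 to 9.7.
- From every 7 days, Visit 3 at day 56: x = 56/5 + (s − 56)/7 + (t − s)/3.5 = 3.2 + t/3.5 − s/7. The conditions give s > about 73 and s ≤ about 200. Counting whole infusions gives days 75-200 (126 days), or Months 2.5 to 6.6. A later Visit 3 moves these by a few days.

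**Example.** Every 5 days, changed to twice weekly on day 120, gives ED 38-46 across the Visit 4 window and 91-99 across the Visit 5 window.

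**Bleed-treatment ED.** Each extra ED before Visit 4 moves both limits later by 1/(1/3.5 − 1/5) ≈ 12 days from every 5 days, or 1/(1/3.5 − 1/7) = 7 days from every 7 days. The interval moves but does not close.

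**The case against.** The footnote asks for at least one visit in range, so Month 6 at ED 28-40 on the less frequent regimens is not an error in itself. Visit 5 satisfies the footnote for both. That stands.

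A recommended increase in frequency need not mean twice weekly: a move from every 7 to every 5 days keeps Visit 5 in range. That also stands, but from every 5 days the only more frequent regimen listed is twice weekly. SAP section 7 mentions a low number of treated bleeds, which suggests few bleed-driven changes, although no count of changes is given.

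The exact days are fragile. These participants bleed, and each treated bleed can add ED. Four extra ED by Month 6 would bring the day-120 example to ED 50 as the Visit 4 window closes. The limits are therefore approximate, though the gap remains for later switch dates.

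The consequence is bounded. The primary endpoint covers the whole study, no SAP analysis depends on a sample at ED 50-75, and the example participant is still tested before and after the range. Suspected loss of efficacy triggers testing (Protocol 8.2.1), and investigators may add visits (Protocol 8). The last two are conditional or discretionary, so they do not supply the scheduled sample.

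Two stronger readings are tempting. One is that every mid-study move to twice weekly misses the range. That is not so: a change at or before Visit 3 can reach ED 50 late in the Visit 4 window, and a change after about day 200 or day 295 has Visit 5 in range. The other is that the optional six-month interim wrongly claims to lie beyond the risk period. Protocol 9.5 says "The risk for inhibitor development is highest during the first 20-50 ED" but never says that six months lies past ED 50, so nothing is contradicted there.

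**Conclusion.** Wrong as written, for a subgroup. For changes to twice weekly at roughly Months 2.5 to 9.7 (from every 5 days) or Months 2.5 to 6.6 (from every 7 days), following the windows cannot meet the footnote or the section 4.1 commitment. Participants on twice weekly from Visit 3 meet it only in about the last week of the Visit 4 window. Those who stay on every 5 or every 7 days are covered at Visit 5.

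The limits rest on full adherence and scheduled infusions only. How many participants would change regimen in these intervals cannot be derived from the documents. The effect is a missing scheduled immunogenicity sample in a range that the protocol itself names; it does not invalidate the primary endpoint.

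**What to change.** Keep the Month 6 immunogenicity sample for everyone. If it was not taken at ED 50-75, take the Visit 5 immunogenicity sample when the diary count shows ED 50-75 instead of by the Month 12 window. Leave the other Visit 5 procedures at Month 12. Label Visits 4 to 6 by month only, in Table 1-1 and Appendix 4, and reword footnote c to match.

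Only the Visit 5 draw should move. Moving the Month 6 draw into ED 50-75 would leave no scheduled inhibitor test between ED 15 and ED 50, which covers most of the period that Protocol 9.5 calls highest risk.

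The cost is wording in the schedule and visit descriptions. The electronic diary records each home injection and transmits in real time, and site contacts are monthly. On twice weekly the range lasts about 26 × 3.5 = 91 days, so about three contacts fall inside it. No sample is added. The downside is a less predictable date for that draw, which for some participants means a separate visit from Month 12.
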